7.1.1 Administrative Procedures

7.1.1.1 Informed Consent

The Investigator must obtain documented consent from each potential subject prior to participating in a clinical trial.

7.1.1.1.1 General Informed Consent

Consent must be documented by the subject's dated signature or by the subject's legally acceptable representative's dated signature on a consent form along with the dated signature of the person conducting the consent discussion.

A copy of the signed and dated consent form should be given to the subject before participation in the trial.

The initial informed consent form, any subsequent revised written informed consent form and any written information provided to the subject must receive the IRB/ERC's approval/favorable opinion in advance of use. The subject or his/her legally acceptable representative should be informed in a timely manner if new information becomes available that may be relevant to the subject's willingness to continue participation in the trial. The communication of this information will be provided and documented via a revised consent form or addendum to the original consent form that captures the subject's dated signature or by the subject's legally acceptable representative's dated signature.

Specifics about a trial and the trial population will be added to the consent form template at the protocol level.

The informed consent will adhere to IRB/ERC requirements, applicable laws and regulations and Sponsor requirements.

7.1.1.2 Inclusion/Exclusion Criteria

All inclusion and exclusion criteria will be reviewed by the investigator or qualified designee to ensure that the subject qualifies for the trial.

7.1.1.3 Medical History

A medical history will be obtained by the investigator or qualified designee. Medical history will include all active conditions, and any condition diagnosed within the prior 10 years that are considered to be clinically significant by the Investigator. Details regarding the disease for which the subject has enrolled in this study will be recorded separately and not listed as medical history.

7.1.1.4 Prior and Concomitant Medications Review

7.1.1.4.1 Prior Medications

The investigator or qualified designee will review prior medication use, including any protocol-specified washout requirement, and record prior medication taken by the subject within 28 days before starting the trial. Treatment for the disease for which the subject has enrolled in this study will be recorded separately and not listed as a prior medication.

7.1.1.4.2 Concomitant Medications

The investigator or qualified designee will record medication, if any, taken by the subject during the trial. All medications related to reportable SAEs and ECIs should be recorded as defined in Section 7.2.

7.1.1.5 Disease Details and Treatments

7.1.1.5.1 Disease Details

The investigator or qualified designee will obtain prior and current details regarding disease status.

7.1.1.5.2 Prior Treatment Details

The investigator or qualified designee will review all prior cancer treatments including systemic treatments, radiation and surgeries.

7.1.1.5.3 Subsequent Anti-Cancer Therapy Status

The investigator or qualified designee will review all new anti-neoplastic therapy initiated after the last dose of trial treatment. If a subject initiates a new anti-cancer therapy within 30 days after the last dose of trial treatment, the 30 days Safety Follow-up visit must occur before the first dose of the new therapy. Once new anti-cancer therapy has been initiated the subject will move into survival follow-up.

7.1.1.6 Assignment of Screening Number

All consented subjects will be given a unique screening number that will be used to identify the subject for all procedures that occur prior to treatment allocation. Each subject will be assigned only one screening number. Screening numbers must not be re-used for different subjects. Any subject who is screened multiple times will retain the original screening number assigned at the initial screening visit.

7.1.1.7 Assignment of Treatment Number

All eligible subjects will receive a treatment number. The treatment number identifies the subject for all procedures occurring after treatment allocation/randomization. Once a treatment number is assigned to a subject, it can never be re-assigned to another subject. A single subject cannot be assigned more than 1 treatment number.

7.1.1.8 Trial Compliance (Medication/Diet/Activity/Other)

Interruptions from the protocol-specified treatment plan for greater than 12 weeks between doses for non-drug-related or administrative reasons require consultation between the investigator and the Sponsor and written documentation of the collaborative decision on subject management. The total volume of study treatment infused will be compared to the total volume prepared to determine compliance with each dose administered. The instructions for preparing and administering study treatment are provided in the Pharmacy Manual. Administration of trial treatment will be witnessed by the investigator and/or trial staff or qualified designee per institutional guidelines and procedures.

7.1.2 Clinical Procedures/Assessments

7.1.2.1 Adverse Event (AE) Monitoring

The investigator or qualified designee will assess each subject to evaluate for potential new or worsening AEs as specified in the Trial Flow Chart and more frequently if clinically indicated. Adverse experiences will be graded and recorded throughout the study and during the follow-up period according to NCI CTCAE Version 4.0 (see Section 11.2). Toxicities will be characterized in terms regarding seriousness, causality, toxicity grading, and action taken with regard to trial treatment.

Please refer to section 7.2 for detailed information regarding the assessment and recording of AEs.

7.1.2.2 Full Physical Exam

The investigator or qualified designee will perform a complete physical exam during the screening period. Clinically significant abnormal findings should be recorded as medical history. A full physical exam should be performed during screening,

7.1.2.3 Directed Physical Exam

For cycles that do not require a full physical exam per the Trial Flow Chart, the investigator or qualified designee will perform a directed physical exam as clinically indicated prior to trial treatment administration.

7.1.2.4 Vital Signs

The investigator or qualified designee will take vital signs at screening, prior to the administration of each dose of trial treatment and at treatment discontinuation as specified in the Trial Flow Chart (Section 6.0). Vital signs should include temperature, pulse, respiratory rate, weight and blood pressure. Height will be measured at screening only.

7.1.2.5 Eastern Cooperative Oncology Group (ECOG) Performance Scale

The investigator or qualified designee will assess ECOG status (see Section 11.1) at screening, prior to the administration of each dose of trial treatment and discontinuation of trial treatment as specified in the Trial Flow Chart.

7.1.2.6 Tumor Imaging and Assessment of Disease

The schedules of tumor imaging and assessment of tumor status are detailed in 7.1.5.4.

7.1.2.7 Tumor Tissue Collection and Correlative Studies Blood Sampling

Please see 4.2.3.2 biomarker research about the detail for tumor tissue collection and correlative studies blood sampling. The time points about samples collection are summarized in 6.0 Study Flowchart.

7.1.3 Laboratory Procedures/Assessments

Details regarding specific laboratory procedures/assessments to be performed in this trial are provided below Laboratory Safety Evaluations (Hematology, Chemistry and Urinalysis)

Laboratory tests for hematology, chemistry, urinalysis, and others are specified in Table 5.

Table 5 Laboratory Tests

Hematology	Chemistry	Urinalysis	Other
Hematocrit	Albumin	Blood	Serum β -human chorionic gonadotropin†
Hemoglobin	Alkaline phosphatase	Glucose	(β -hCG)†
Platelet count	Alanine aminotransferase (ALT)	Protein	PT (INR)
WBC (total and differential)	Aspartate aminotransferase (AST)	Specific gravity	aPTT
Red Blood Cell Count	Lactate dehydrogenase (LDH)	Microscopic exam (If abnormal)	Total triiodothyronine (T3)
Absolute Neutrophil Count	Uric Acid	results are noted	Free tyroxine (T4)
Absolute Lymphocyte Count	Calcium	Urine pregnancy test †	Thyroid stimulating hormone (TSH)
	Chloride		
	Glucose		
	Phosphorus		Blood for correlative studies
	Potassium		
	Sodium		
	Magnesium		
	Total Bilirubin		
	Direct Bilirubin (If total bilirubin is elevated above the upper limit of normal)		
	Blood Urea Nitrogen		

† Perform on women of childbearing potential only. If urine pregnancy results cannot be confirmed as negative, a serum pregnancy test will be required.

Laboratory tests for screening or entry into the Second Course Phase should be performed within 10 days prior to the first dose of treatment. After Cycle 1, pre-dose laboratory procedures can be conducted up to 72 hours prior to dosing. Results must be reviewed by the investigator or qualified designee and found to be acceptable prior to each dose of trial treatment.

7.1.3.1 Blood Collection

- (1) On every occasion of collecting blood for exploratory biomarker research, 10 ml of blood will be collected through sodium citrate-containing tubes.
- (2) The blood samples will be sent to Lab for further processing within 30 minutes.
- (3) 10 ml blood for collection of plasma (in aliquots) and peripheral blood mononuclear cells (PBMCs) through Ficoll-Hypaque centrifugation. The PBMCs will be separated into two equal pellets: one to be freshly frozen; the other kept in RNAZol.

The time points for blood sampling (Correlative Studies Blood Collection) are described in Section 6.0 – Trial Flow Chart.

7.1.4 Other Procedures

7.1.4.1 Withdrawal/Discontinuation

When a subject discontinues/withdraws prior to trial completion, all applicable activities scheduled for the final trial visit should be performed at the time of discontinuation. Any adverse events which are present at the time of discontinuation/withdrawal should be followed in accordance with the safety requirements outlined in Section 7.2 - Assessing and Recording Adverse Events.

7.1.4.2 Blinding/Unblinding

Not applicable.

7.1.5 Visit Requirements

Visit requirements are outlined in Section 6.0 - Trial Flow Chart. Specific procedure-related details are provided above in Section 7.1 - Trial Procedures.

7.1.5.1 Screening

Approximately 28 days prior to treatment, potential subjects will be evaluated to determine that they fulfill the entry requirements as set forth in Section 5.1. Screening procedures may be repeated.

- a. The candidate patient will be screened according to the 5.1 Entry Criteria.
- b. Laboratory tests performed according to Table 5 and Flow Chart 6.1.
- c. Tumor imaging performed according to Flow Chart 6.1.

7.1.5.2 Treatment Period (also detailed in 6.1 Study Flow Chart):

- a. During the period of adjuvant cisplatin-CRT:
 - i. The patient will be seen on a weekly basis until 2 weeks after completing CRT.
 - ii. The patient will be evaluated for clinical symptoms and signs, hemogram, and biochemistry panel including bilirubin, AST, ALT, BUN, creatinine, Na, K, Ca, Mg, and other abnormalities found at screening check.
- b. During the period of adjuvant pembrolizumab therapy:
 - i. The patient will be seen on a 3-weekly basis for a total of 54 weeks.
 - ii. The patient will be evaluated for clinical symptoms and signs, hemogram, biochemistry panels including bilirubin, AST, ALT, ALP, gamma-GT, LDH, albumin, BUN, creatinine, Na, Cl, K, Ca, Mg, P, and glucose, and endocrine function (every 2 cycles) including TSH, T3, fT4, ACTH and cortisol.
 - iii. Pregnancy Test – Urine or Serum beta-HCG (for woman only), coagulation test with PT/INR and aPTT, and urinalysis will be checked every 2 cycles.
 - iv. Tumor imaging includes CT scan (of neck, chest, and abdomen) and esophagoscopy every 4 cycles of pembrolizumab.

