Duration of Participation	
Subjects need to sign the informed consent form to be enrolled into this trial.After a screening phase up to 28 days, each subject will receive adjuvant weekly cisplatin -CRT (cisplatin, 30mg/m²/week x 2; radiotherapy, 180-200 cGy/fraction x 10-13) followed by pembrolizumab (200mg/3 weeks x 18) (approx. a total of 56 weeks).Treatment will continue until the completion of the planned cisplatin-CRT plus 18 cycles of pembrolizumab, or until recurrent disease, unacceptable adverse events, intercurrent illness that prevents further administration of treatment, investigator's decision to withdraw the subject, subject withdrawal of consent, pregnancy of the subject, noncompliance with trial treatment, or administrative reasons requiring cessation of treatment.To detect the tumor recurrence, all patients will be evaluated by pertinent evaluation and imaging studies every 4 cycles of pembrolizumab during treatment phase, then every 3 months for post-treatment year-1 to year-2, and every 6 months for post-treatment year-3 and year-4.Subjects who discontinue for reasons other than recurrent disease will have post-treatment follow-up visits for monitoring disease status as if they were still on treatment until recurrent disease, initiating a non-study cancer treatment, withdrawing consent from study participation, or becoming lost to follow-up.All subjects will be followed (e.g., by telephone or visit) for overall survival until death, withdrawal of consent from study participation, or the end of the study, whichever comes first. After the end of study treatment, each subject will be followed for 30 days for adverse event monitoring. Serious adverse events will be

	collected for 90 days after the end of treatment or for 30 days after the end of treatment if the subject initiates new anticancer therapy, whichever is earlier.
Estimated average length of treatment per patient	56 weeks

[figure not shown]

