4.2.4 Rationale for Endpoints

4.2.4.1 Efficacy Endpoints

1. The primary endpoint is the 1-year RFS rate.
2. The secondary endpoints include median RFS, 3-year OS rate, median OS time, 3-year RFS rate, safety and toxicity.

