8.2.2 Definition of Variables

8.2.2.1 Recurrence-free survival is the time from enrollment to disease recurrence or the last follow-up (censored). Recurrence is defined by suspicious lesion noted by tumor imaging according to RECIST 1.1. Tissue proof for suspicious lesion is recommended if it is feasible.

8.2.2.2 Overall survival is the time from enrollment to death of any cause or the last follow-up (censored).

8.2.2.3 Evaluation of Toxicity: The incidence and severity of toxicity will be summarized according to the NCI Common Toxicity Criteria Version 4.0.

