8.2.3 General Statistical Consideration

8.2.3.1 All statistical analyses will be performed for intent-to-treatment population.

8.2.3.2 The survival estimates will be derived from Kaplan and Meier curves.

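### No scan is fixed at 12 months: first-year imaging follows pembrolizumab cycle count, so the last look before the 1-year RFS landmark varies with start delay and dose holds

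*Combined protocol and SAP*

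**What the plan says.** Section 4.2.4.1: "The primary endpoint is the 1-year RFS rate". Section 8.2.2.1 sets the clock and the event: "Recurrence-free survival is the time from enrollment to disease recurrence or the last follow-up (censored", and "Recurrence is defined by suspicious lesion noted by tumor imaging according to RECIST 1.1". Section 8.2.3.2 gives the method: "The survival estimates will be derived from Kaplan and Meier curves". Enrollment is not tied to consent or to the start of CRT.

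On-treatment imaging follows cycle number in three places:
- Section 7.1.5.2(b.iv): "Tumor imaging includes CT scan (of neck, chest, and abdomen) and esophagoscopy every 4 cycles of pembrolizumab".
- Section 1.0: "all patients will be evaluated by pertinent evaluation and imaging studies every 4 cycles of pembrolizumab during treatment phase".
- The flow chart in 6.1 puts the imaging tick in the cycle-4 column, and that block repeats.

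Scans by calendar date begin only after treatment (1.0, 6.1, 7.1.5.4). Planned treatment is about 56 weeks, so a patient treated to plan passes month 12 while still on the cycle-based schedule.

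Subjects who stop early for reasons other than recurrence have "post-treatment follow-up visits for monitoring disease status as if they were still on treatment" in section 1.0, whereas the post-treatment column of 6.1 says every 3 months. Neither rule is anchored at month 12.

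**The concern.** A recurrence without symptoms that arises after the last scan before month 12 is found, and dated, after month 12. The Kaplan-Meier estimate at 1 year then treats that patient as recurrence-free. The length of this unobserved stretch is set by how soon pembrolizumab starts and whether doses are held, not by the endpoint. It can differ between patients, and it could differ from the historical series that supplies the 32.3% benchmark. With about 24 evaluable patients, a shift of one patient is not negligible.

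**Working it through.** **The plan's own figures.**
- Treatment length: 2 weeks of CRT + 18 × 3 weeks = 56 weeks. This matches section 1.0 and leaves no gap between CRT and pembrolizumab.
- Sample size (8.2.1): exact binomial, 32% v 60%, two-sided 5%. With n = 24 and success at 13 or more, the upper-tail error is 0.020 and power is 0.787, close to the stated 80%.

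**Inputs.**
- Screening, 0 to 4 weeks (1.0: "After a screening phase up to 28 days, each subject will receive adjuvant weekly cisplatin").
- CRT, 10 to 13 fractions at 5 per week = 2.0 to 2.6 weeks (5.2.2.1).
- Gap from CRT to pembrolizumab, 0 to 4 weeks (5.2.2.2).
- Cycle length, 3 weeks. One year = 52.18 weeks.

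**First pembrolizumab dose.** From CRT start: 2.0 + 0 to 2.6 + 4 = week 2.0 to 6.6. From consent, adding screening: week 2.0 to 10.6.

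**Fourth scan, no interruption.**

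| Reading of every 4 cycles | CRT clock | Consent clock |
|---|---|---|
| Day 1 of cycle 16 (start + 45) | 47.0 to 51.6 | 47.0 to 55.6 |
| After 16 completed cycles (start + 48) | 50.0 to 54.6 | 50.0 to 58.6 |

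Section 5.2.2.2(b) puts assessments before the Day 1 dose, which favors the first row. A tick in the cycle-4 column does not settle the day within the cycle, so the second row remains open.

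**Share of fourth scans after week 52.18, delays uniform (assumption).** The start delay must exceed 52.18 − 45 = 7.18 weeks (Day-1 reading) or 52.18 − 48 = 4.18 weeks (completed-cycle reading). Hand check with CRT at its mean of 2.3 weeks:
- Day 1, CRT clock: the maximum delay of 6.6 is below 7.18, so 0%.
- Day 1, consent clock: gap + screening > 4.88, so (8 − 4.88)²/32 = 0.30 (simulation 31%).
- Completed, CRT clock: gap > 1.88, so (4 − 1.88)/4 = 53%.
- Completed, consent clock: gap + screening > 1.88, so 1 − 1.88²/32 = 89%.

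When the fourth scan is late, the third is the last look before month 12. Scans are 4 × 3 = 12 weeks apart, so the unobserved stretch can reach 12 weeks. On the Day-1 reading with the CRT clock it is only 52.18 − 51.6 = 0.6 to 52.18 − 47 = 5.2 weeks.

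**Effect on the apparent rate.** Apparent rate = mean over start delays of p^(t/52.18), where t is the week of the last scheduled scan before month 12. This assumes constant hazard, detection only at scheduled scans, uniform delays and no holds (2,000,000 draws). For example, t = 47 gives 0.32^(47/52.18) = 35.8%.

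| Reading | True 32%, CRT / consent clock | Excess in 24 patients |
|---|---|---|
| Day 1 | 34.1% / 35.5% | 24 × 0.021 = 0.5 / 24 × 0.035 = 0.8 |
| Completed cycles | 36.9% / 38.6% | 24 × 0.049 = 1.2 / 24 × 0.066 = 1.6 |

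On the Day-1 reading a true 60% appears as 61.7% / 62.8%. A falling hazard fitted to the plan's 6.7-month median and 32.3% has Weibull shape ln(ln 0.323/ln 0.5)/ln(12/6.7) = 0.839. It gives 33.8% / 34.9% for a true 32%, so the hazard shape matters little.

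**Interruptions.** Suppose one full 3-week interruption defers all later cycles (assumption). On the Day-1 reading the fourth scan then moves to week 50 to 54.6 or 50 to 58.6, and 53% or 89% are late.

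**The case against.** The strongest objection is that the benchmark is itself an observed rate. If the historical patients were scanned every 13 weeks at random phase (an assumption), the same arithmetic makes a true 32% read about 37%. That is more than this trial's 34.1 to 35.5% on the Day-1 reading. This stands. A reader might infer that the schedule biases the trial toward success, or that the false-positive probability rises from 0.020 to 0.034 to 0.047 (13 or more of 24, Day-1 reading). Both inferences need a benchmark free of detection delay, and the documents give no scan schedule for that series.

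A reader might also infer that one scan decides 1-year status. It does not: Kaplan-Meier uses event dates throughout the year. A late fourth scan matters only for patients still recurrence-free near cycle 16, about 0.32 × 26 = 8 under the null.

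Nor do the documents show that interruptions must delay scans. Section 5.2.1.2 gives 3 weeks as a maximum for unrelated interruptions and does not say whether doses are skipped or deferred.

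Three-weekly visits (7.1.5.2), imaging of symptomatic regions (6.1, footnote e) and unscheduled procedures (7.1) will bring some detections forward. For early stoppers, 12-weekly and 3-monthly scans are nearly the same interval, so that conflict is minor.

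What survives is narrower. The start delay that the protocol permits can by itself move the fourth scan across month 12, except on the Day-1 reading with the CRT clock. Nothing in the plan anchors a scan there.

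**Conclusion.** The point holds as a cheap, optional improvement. The distance between the last scan and the 1-year landmark is left to start delay, to an undefined enrollment date and to an ambiguous cycle rule. At most this adds about 2 to 3.5 percentage points to a true 32% on the Day-1 reading, or 5 to 6.5 points on the completed-cycle reading. Detection only at scheduled scans is what makes these upper limits. Uniform delays, constant hazard and no holds are working assumptions, and deferred doses could move scans later. The direction of net bias against 32.3% is unknown, so the comparison is not shown to be invalid.

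**What to change.** **Sections 6.1 and 7.1.5.2.** Schedule first-year imaging by calendar time from enrollment, for example weeks 13, 26, 39 and 52, regardless of cycle number, holds or early discontinuation. Give the 12-month scan a narrow window, for example ± 2 weeks. Define enrollment as a dated event. Reconcile section 1.0 with 6.1 on scans for early stoppers.

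**Section 8.2.2.1.** State how the windowed scan determines 1-year status. Also state what happens if it is missed: for example, a later clear scan confirms status; otherwise censor at the last clear scan and count the patient as an event in a sensitivity analysis.

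**Dating rule.** Assign a recurrence first seen in the window to nominal month 12 in the primary estimate only if the historical 32.3%, which comes from the center's own series, is re-derived under the same rule. Correcting one side alone could tilt the test against the treatment. Otherwise use actual detection dates as primary and report the nominal-date version as a sensitivity analysis. With actual dates the window should close by month 12. A scan in week 53 or 54 would leave week 39 as the last look, where 0.32^(39/52.18) = 42.7%; a scan in weeks 50 to 52 gives 33.6 to 32.1%.

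**Cost.** A few sentences. First-year scans stay at four, and sample size and dosing are unchanged. Some scans will not coincide with a dosing visit. On the Day-1 reading the first scan comes up to 13 − 11 = 2 weeks later than now for the earliest starters. For the latest starters on the consent clock it falls only 13 − 10.6 = 2.4 weeks after the first pembrolizumab dose.
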